The purpose of this study is to evaluate the effects that maternal B+N maintenance have on the neurobehavioral development of the fetus and infant. To accomplish this, we will study a sample of  $n=80$  (considering a recidivism rate of 50% for  $n=40$  protocol completers) opioid dependent pregnant women that will receive B+N as part of substance abuse treatment at a comprehensive care treatment facility for pregnant and parenting women with substance use disorders, or stable patients receiving B+N from other treatment providers who are willing to a) complete the Addiction Severity Index (ASI) around the time of consent, b) consent to a review of medical records, c) leave weekly research urines for the study team and d) plan for delivery at the JHBMC hospital. A matched sample of  $n=80$  (considering a recidivism rate of 50% for  $n=40$  protocol completers) methadone maintained women will be recruited as a comparison sample. Fetal neurobehavior and maternal physiology will be assessed, via an established maternal-fetal data acquisition system, at 4 points during gestation: 24, 28, 32 and 36 weeks. Infant birth parameters and NAS spectrum display will be evaluated at birth, and infant neurodevelopment will be assessed during the first month of life. We will compare the neurodevelopment of the B+N-exposed fetuses and infants to that of the comparison group of methadone and a historical (2012-2016) group of buprenorphine-only exposed fetuses and infants. Additionally, among a subsample of participants who wish to and are eligible to breastfeed their infants, we will evaluate maternal plasma, breast milk and infant plasma concentrations of buprenorphine, naloxone and their major metabolites.

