*Ascertainment of illicit substance use/licit substance misuse:* Quicktest urine screening, which will include testing for buprenorphine (10 ng/mL), amphetamines (1000 ng/mL), barbiturates (300 ng/mL), benzodiazepines (300 ng/mL), cocaine (300 ng/mL), methadone (300 ng/mL), methamphetamines (1000 ng/mL), opiates (300 ng/mL), oxycodone (100 ng/mL), and THC (50 ng/mL), for a total of once weekly screening, will occur for CAP participants and those from other treatment programs. These urine toxicology screens will be performed by research staff. Participants will undergo urine toxicology screening at the time of each fetal monitoring session. Urine toxicology screening that is positive, i.e. representative of illicit substance use or licit substance misuse, at the time of fetal testing will result in cancellation of the fetal monitoring procedures for that day, with the exception of marijuana (see above).

*Ascertainment of other substances.* Alcohol is a well-known fetal teratogen, and chronic fetal exposure to alcohol will be excluded in the study populations. Any woman meeting DSM V or ASI criteria for alcohol use disorder will not be enrolled. We will also attempt to identify women using alcohol acutely; recent alcohol use will be verified with participant interview. Positive clinical screens for alcohol use will also be tracked via chart review. Women having evidence of or reporting recent alcohol use more than three times during the period of study enrollment will be removed from the protocol; however alcohol use emerged as a disenrollment criteria in only one participant in the prior study, likely due to our exclusion of alcohol use disordered participants based on ASI screening. In contrast to the low levels of alcohol use in our participants, cigarette smoking is routine, reflecting the larger CAP clientele: 88.5% use nicotine. Self-report data will be collected from each participant regarding the average number of cigarettes smoked per day upon enrollment and at each testing point. Women will be asked to refrain from smoking for 2 hours prior to each maternal-fetal recording. Nicotine withdrawal is unlikely in this time frame, and pregnant women are less likely to report any nicotine withdrawal in the first 24 hours of abstinence than non-pregnant women (Ussher, 2012).

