### **Maternal-fetal monitoring protocol**

[figure not shown]
[figure not shown]
Maternal-fetal monitoring will occur at the 24th, 28th, 32nd and 36th weeks of gestation. These periods reflect the most intensive developmental trajectories in fetal neurobehaviors, which become more complex as term advances, with a shift in the steepness of the developmental trajectory in most parameters between 28 and 32 weeks ([name], 2004). Quality continuous fetal heart rate monitoring is difficult prior to 24 weeks due to movement artifact. Monitoring sessions will last for 60 minutes and be conducted at 9 AM (the time of trough maternal B+N level) and again at 2 ½ hours after a single sublingual dose of B+N which corresponds to the time of peak maternal medication level. Women who are recruited for study participation will have their dose administered around 10 AM for 1 week prior to the time of fetal testing, and be on a stable dose of B+N during that time period. On the day of fetal testing, women will be instructed to eat breakfast 1 ½ hours prior to testing to control variation in blood glucose. Concurrent maternal-fetal monitoring will be digitized at 1000 Hz using an external analog to digital board using streaming software (Snapstream, HEM, Inc). The methodology and data processing techniques described have been used in our prior studies and are comprehensively described elsewhere ([name], 2015).

*Fetal data.* Fetal data will be generated from a Toitu (MT516) fetal actocardiograph, which detects fetal movement (FM) and fetal heart rate (FHR) through a single wide array transabdominal Doppler transducer and processes this signal through a series of filtering techniques. The actograph detects FM by preserving the remaining signal after band-passing frequency components of the Doppler signal that are associated

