Study duration and the number of study visits depends on when during gestation (up to 34 weeks of gestational age) the participant enters the protocol. One hour long maternal-fetal monitoring sessions will occur up to 8 times, twice on 4 separate days at monthly intervals (i.e., 24, 28, 32 and 36 weeks). The number of monitoring visits depends on the gestational age at enrollment; participants enrolling after 24 weeks will have fewer visits. There are no study visits for neonatal testing, as all data are abstracted from neonatal charts as standard of care. Infants will be enrolled for 1 month after birth, and make 3 study visits (days 3, 14 and 30). For those participants enrolled in the lactation arm, study visits will occur on days 2,3,4,14 and 30 postpartum for sampling.

c. Blinding, including justification for blinding or not blinding the trial, if applicable.

This trial is not an open label trial; therefore, there is no blinding of study participants.

d. Justification of why participants will not receive routine care or will have current therapy stopped.

All CAP participants will receive standard substance use disorder, prenatal and pediatric care through the CAP program and in the newborn nursery or NICU. All participants from other treatment programs will receive care through their providers in those programs.

e. Justification for inclusion of a placebo or non-treatment group. NA

f. Definition of treatment failure or participant removal criteria.

There are several scenarios under which participants may terminate the study voluntarily or as a result of safety or compliance concerns. These include: patient choice (e.g., does not like buprenorphine-naloxone); voluntary or enforced discharge from the CAP or other treatment program (e.g., from incarceration, relocation, violation of CAP rules); physician choice (e.g., toxicity or side effects related to buprenorphine-naloxone); and ineligibility (e.g., violation of the study protocol, missing 5 consecutive days of buprenorphine-naloxone dosing, loss of pregnancy, development of fetal or maternal health condition).

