## 5. Inclusion/Exclusion Criteria

Fetal, Neonatal and Infant protocol: *Inclusion criteria:* 1. Current opioid use disorder (OUD) as defined by DSM 5 criteria 2.18-44 years of age with singleton pregnancies, generally uncomplicated by conditions that jeopardize pregnancy outcome 3. Gestation less than 34 weeks

**Exclusion criteria:** 1. Complications of pregnancy, including gestational diabetes, polyhydramnios, hypertension, placenta previa or significant risk of preterm delivery; 2. Evidence of fetal malformation detected by prenatal ultrasound; 3. Significant general maternal health problems that can affect fetal functioning, including Type I or gestational diabetes, alterations in thyroid functioning, HIV infection or hypertension; 4 Significant maternal psychopathology that would preclude informed consent, such as unstable schizophrenia; 5. Alcohol use disorder per DSM 5 criteria; 6. Significant benzodiazepine use which would portend seizure activity during the induction period. This will be determined for all women reporting benzodiazepine use at the time of program intake by the project psychiatrist(s). 6. For the B+N group: Women stable on methadone maintenance (defined as more than 3 consecutive days of dosing); 7. For the B+N group: Women coming to treatment reporting “street” methadone use (for more than 3 consecutive days); 8. Women planning for adoption of their infant.

**Breastmilk protocol:** 10 B+N exposed infants and their mothers from the fetal study who meet criteria for breastfeeding (i.e. illicit drug use/licit drug misuse abstinence in the last 90 days prior to delivery or counselor endorsement of breastfeeding in the case of abstinence 30-90 days prior to delivery, HIV negative status, no concurrent prescription medication use that is contraindicated in lactation, and legal custody of their infant at delivery) will be enrolled.

**Inclusion criteria:** 1. B+N maintained mother, enrolled in parent study. 2. Free of illicit drug use and licit drug misuse after 36 weeks gestation or 30-90 days prior to delivery by standardized urine toxicology drug screening and drug treatment compliant. 3. Delivery at 37 weeks or later determined by second trimester ultrasound which is standard of care at the facility of recruitment.

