*Infant variables.* Infant testing using the NNNS generates 13 summary scores (habituation, attention, handling, quality of movement, regulation, non-optimal reflexes, asymmetric reflexes, stress/abstinence, arousal, hypertonia, hypotonia, excitability and lethargy) that have been normatively described for both substance exposed and non-exposed infants (Tronick, 2004). Exploratory data analysis techniques will be used to determine distributions for each measure to determine how many of these will be used in the final analysis.

*Breastmilk variables:* Concentrations of B+N and major metabolites in breast milk, maternal and infant plasma

b. Statistical plan including sample size justification and interim data analysis.

*Fetal studies:* Individual analyses will be performed for three cardiac measures (FHR, FHR variability and accelerations) and two motor variables (overall activity, bout duration), and two synthetic measures (event and time series-based FM-FHR coupling, as described in the Procedures section. We will also evaluate effects of BN on maternal physiological function (heart period, respirations, cardiac vagal tone, skin conductance, and blood pressure).

Models for aims 1 and 2 will be longitudinal mixed effects linear regression models with random intercepts (Fitzmaurice, 2011). Additional models with fetal sex interactions will be fit to evaluate whether boys are differentially affected by either exposure, as we have observed in previous evaluating neurobehavior in methadone exposed infants (Jansson, 2010). Additionally, all analyses will be adjusted for maternal age, race, and non-opioid substance use.

For Hypothesis 1A, we will fit a model where the outcome for the  $i$ th individual at the  $j$ th timepoint ( $y_{ij}$ ) =  $\beta_0 + \beta_1 \text{peak} + \beta_2 \text{p}_2 - \text{p}_1 + \epsilon_{ij}$ , and  $\beta_1$  represents the difference, across timepoints, in the outcome between peak and trough measurements. For Hypothesis 1B, we will fit a similar model,  $y_{ij} = \beta_0 + \beta_1 \text{peak} + \beta_2 \text{time} +$

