$\beta_3\text{peak} * \text{time} + \beta_4 \cdot \text{pX4\_p} + \varepsilon_{ij}$ , where  $\beta_3$  represents the rate of change in the difference in outcome between peak and trough over time. For Hypothesis 1C, we will fit a model where  $y_{ij} = \beta_0 + \beta_1\text{peak} + \beta_2\text{BN} + \beta_3\text{peak} * \text{BN} + \beta_4 \cdot \text{pX4\_p} + \varepsilon_{ij}$ , where  $\beta_3$  represents the between-treatment (BN-Methadone) or (BN-Buprenorphine) difference in peak-trough differences. Additionally, we will fit a model with a 3-way interaction between peak, time, and BN to determine if changes over time in peak-trough differences vary between BN and Buprenorphine.

For Hypothesis 2A, we will fit models separately for peak and trough measures where  $y_{ij} = \beta_0 + \beta_1\text{BN} + \beta_2 \cdot \text{pX2\_p} + \varepsilon_{ij}$  where  $\beta_1$  represents the difference in outcome between BN and Bup. We will also fit models where  $(y_{ij}) = \beta_0 + \beta_1\text{BN} + \beta_2\text{time} + \beta_3\text{BN} * \text{time} + \beta_4 \cdot \text{pX4\_p} + \varepsilon_{ij}$ , and  $\beta_3$  represents the difference in outcome trajectory over time between BN and Buprenorphine. For Hypothesis 2B, we will fit a model similar to 2A but only using data from 36 weeks to compare methadone and BN.

*Neonatal study:* For hypothesis 3A, we will use descriptive statistics to characterize NAS in BN-exposed infants, as measured by mean daily NAS scores on days 1-4 of life, highest NAS score, amount of medication (morphine sulfate, mg) required to treat NAS, number of days treated for NAS, and total days hospitalization. For hypothesis 3B, we will fit models of NAS severity (measured by Day 3 Finnegan scores, total medication used to treat NAS, total days of NAS treatment and total days of hospitalization), as a function of BN exposure (compared to methadone exposure), adjusting for maternal age, race, and non-opioid substance use. The models for hypothesis 3C will be analogous, but with buprenorphine exposure as the comparator. For hypothesis 3D, we will examine additional predictors of NAS severity including infant sex (Warren, 2015), daily and cumulative dose of BN, other medications including SSRIs (dosage and categorical), illicit drug use based on number of “dirty” urines and specific substance exposures, cigarette smoking (cigarettes per day and CO levels).

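### The Hypothesis 2A level model has no gestational-age term, so the B+N versus historical buprenorphine difference is confounded by fetal age if the two groups' visit mixes differ

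*Combined protocol and SAP*

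**What the plan says.** The statistical plan (Section 7b, Fetal studies) states: "Models for aims 1 and 2 will be longitudinal mixed effects linear regression models with random intercepts". It adds that "all analyses will be adjusted for maternal age, race, and non-opioid substance use". Gestational week is not on that list.

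For the comparison with buprenorphine-only it continues: "For Hypothesis 2A, we will fit models separately for peak and trough measures where" the right-hand side is an intercept, a B+N indicator and a covariate term. The coefficient on B+N (beta1) is defined as the outcome difference between the two groups. The covariate term is garbled in the converted text. A second 2A model adds time and B+N x time, and the plan names only the interaction (beta3, the trajectory difference) as its target.

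Other sections bear on the point:

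- Maternal-fetal monitoring protocol: outcomes follow developmental trajectories across these weeks, "with a shift in the steepness of the developmental trajectory in most parameters between 28 and 32 weeks".
- Section 5: the entry limit is "Gestation less than 34 weeks".
- Section 4b: "participants enrolling after 24 weeks will have fewer visits".
- Section 4a: a positive urine screen, marijuana excepted, "will result in cancellation of the fetal monitoring procedures for that day".
- Section 1: the comparator is "a historical (2012-2016) group of buprenorphine-only exposed fetuses and infants". Section 2 calls the methadone group matched and does not say so of this one.

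**The concern.** Exposure is a between-woman contrast. A random intercept absorbs stable differences between women. It does not remove a difference between groups in the weeks at which they were recorded. If one group is seen later in pregnancy, part of beta1 is normal fetal development.

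Hypothesis 2a expects either no difference or a more favourable profile with B+N. A shift in one direction could create an apparent advantage, and a shift in the other could hide a real difference. The historical recordings already exist, so their timing cannot be changed and any correction must come from the analysis.

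**Working it through.** **The plan's own figure.** For hypothesis 2 the plan gives a detectable difference of 4.12 with SD 6.49 (peak fetal heart rate), alpha .05 and 80% power. Two-sided, n per group = 2 x (1.960 + 0.842)^2 x (6.49/4.12)^2 = 38.95, so 39. With 40 per group, power is 0.810 (normal) or 0.801 (t, 78 df). The figure reproduces and is not in dispute.

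**Inputs.** From the documents: 40 per group, SD 6.49, visits at 24, 28, 32 and 36 weeks. Assumed, because the documents give none of them: drift d of 0.25 to 1 bpm per week (1 means 12 bpm over the window), intraclass correlation r of .3 to .7, the visit mixes, and bpm as the unit of 4.12.

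**Formula.** With no time term, a random-intercept model weights a woman with m recordings by w(m) = m / (1 + (m - 1)r). With no true group effect, bias in beta1 = d x (difference between groups in weighted mean gestational week). SE^2 = 6.49^2 x (1/sum of w in group 1 + 1/sum of w in group 2). Type I error = P(|Z + bias/SE| > 1.96).

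**Worked case: r = .5, week 24 missing in 40% versus 20%.** w(4) = 4/2.5 = 1.6, with mean week 30. w(3) = 3/2 = 1.5, with mean week 32.

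- Group 1: 30 + 2 x (0.4 x 1.5)/(0.6 x 1.6 + 0.4 x 1.5) = 30 + 1.2/1.56 = 30.769.
- Group 2: 30 + 2 x (0.2 x 1.5)/(0.8 x 1.6 + 0.2 x 1.5) = 30 + 0.6/1.58 = 30.380.
- Difference 0.389 week, so the bias is 0.389 bpm at d = 1 and 0.097 at d = 0.25.
- SE = 6.49 x sqrt(1/62.4 + 1/63.2) = 1.16. At d = 1, bias/SE = 0.336 and type I error is 6.3%.

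**Range over d and r.**

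| Visit mix | Bias (bpm) | Share of 4.12 | Type I error |
|---|---|---|---|
| Equal | 0 | 0% | 5% |
| Week 24 missing, 30% vs 20% | 0.05-0.20 | 1-5% | 5.0-5.4% |
| Week 24 missing, 40% vs 20% | 0.10-0.39 | 2-10% | 5.1-6.6% |
| Week 24 missing, 50% vs 0% | 0.24-0.98 | 6-24% | 5.4-15% |
| Weeks 24 and 28 missing, 50% vs 0% | 0.4-1.9 | 10-46% | 7-37% |

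With variance components estimated (REML simulation, 10,000 replicates per cell), type I error is 4.9-6.4% in the third row and 4.9-13.4% in the fourth. The table is not a bound. If every B+N woman's first visit were at 32 or 36 weeks (half each) and every historical woman's at 24, the bias would reach 4.9 bpm at d = 1.

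**With a four-level visit factor.** Bias is 0 in every row. The SE widens by less than 0.5% when only week 24 is lost, about 1% when weeks 24 and 28 are lost, and up to 8% in the extreme case.

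**Linear time instead of a factor.** Suppose the drift is 1 bpm per week to week 30 and flat afterwards. At 40% versus 20%, the bias is 0.25-0.26 with no term, 0.08 with linear week, 0.09-0.10 for the week-30 contrast from the planned B+N x time model, and 0 with the factor.

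**Hypothesis 1C.** Its peak x B+N coefficient compares recordings on the same day, so a gestational main effect cancels when both sessions are present. It shifts only if the peak-trough gap changes with gestation, which Hypothesis 1b predicts. For an assumed change of 0.1 to 0.35 bpm per week, the bias at 40% versus 20% is 0.351 x that change, or 0.04-0.12 bpm (1-3% of the 4.23 in the power section). At 50% versus 0% it is 0.857 x that change, or 0.09-0.30 bpm (2-7%).

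**The case against.** The best reply is that the plan fits a second 2A model with time and B+N x time to the same data. Its B+N contrast at week 30 has no bias under linear drift, and about 2% of 4.12 under the bent drift above at 40% versus 20%. This stands as a real limit on the harm. But the plan does not name that contrast as an estimand and states no centring for time, so the model's B+N coefficient is a contrast at an unspecified time zero. The statement in Section 7b that the analyses are not exhaustive does not alter a model that is written out.

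Second, imbalance may be small. Section 3 says eligibility is essentially the same across projects, that earlier studies recruited from the same programme, and that the assessment paradigm is shared. Section 4a does not say that a cancelled session cannot be rescheduled. Against this, similar eligibility does not fix entry week, and the B+N group may now include stable patients of other providers. The documents do not settle the matter.

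Third, the unreadable covariate term might contain time. That cannot be excluded. It is unlikely, because the named adjusters omit week and the plan writes time as its own term in the 1B and 2A trajectory equations.

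A reader might also infer that random intercepts alone invalidate the detectable trajectory differences of .35 and .32 per week. The documents do not support that: those figures came from simulations whose variance structure is not described, and the question is separate from visit mix.

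**Conclusion.** The point holds conditionally. As printed, the 2A level model does not protect beta1 from a between-group difference in gestational timing, and the design permits such a difference. Among the illustrated cases in which only week 24 is lost, the distortion is negligible to modest. It becomes material if one group also loses week 28 and drift is steep. All these sizes rest on assumed drift, correlation and visit mix.

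A reader might infer that beta1 is biased, or that B+N women were seen later. The documents show neither. With equal mixes the bias is zero, and no section reports either group's visit distribution. The stated power is unaffected. Hypothesis 1A (no group term) and Hypothesis 2B (36 weeks only) are not exposed to visit mix, and 1C is only a minor case. The change should be made because it is nearly free and the historical visit pattern cannot be altered.

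**What to change.** 1. Add gestational visit (24, 28, 32, 36) as a four-level factor to the Hypothesis 2A level model, at both peak and trough. A factor is preferable to linear week because the protocol itself describes a change in steepness.
2. Report the number of recordings per visit week by group.
3. If the B+N x time model is used for the level comparison instead, centre time, name the week at which the B+N contrast is reported, and note that linear time leaves some bias if the trajectory bends.
4. Minor: in Hypothesis 1C add visit and peak x visit, for both comparators. A visit main effect alone does not remove the exposure. The planned three-way model partly covers this, for buprenorphine only.

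The cost is analysis-plan wording and no new data. The 2A model gains three terms, with the loss of precision shown in the working. Hypothesis 1C gains six terms, with an SE less than 1% wider in the week-24 cases examined.

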### 2. Objectives (include all primary and secondary objectives)

*Aim 1:* Determine the acute effects of B+N and methadone exposure on the fetus by comparing fetal neurobehavior at times of peak and trough maternal B+N levels during the second half of gestation (24,28,32 and 36 weeks).

*Hypothesis 1a:* Fetal heart rate and motor activity patterns indicative of fetal well-being will be attenuated when maternal circulating B+N and methadone is at its peak as compared to trough concentration.

*Hypothesis 1b:* Differentials in fetal heart rate and motor activity patterns between peak and trough will increase over the course of gestation as neurobehavioral development becomes more organized.

*Hypothesis 1c:* The differential in fetal heart rate and motor activity patterns at peak and trough will be reduced in fetuses of B+N maintained mothers as compared to a matched cohort of methadone exposed fetuses, and will show either no difference or greater attenuation when compared to buprenorphine-only exposed fetuses.

*Aim 2:* Evaluate the development of the B+N-exposed fetus, and compare this with two other treatment exposures (a matched prospective methadone maintained group and a recent historical buprenorphine-only group).

*Hypothesis 2a.:* Fetal heart rate and motor activity patterns indicative of greater fetal well-being, and their developmental trajectory, will either not differ between B+N and buprenorphine-only groups at 24, 28, 32 and 36 weeks gestation, or they will be indicative of more optimal neurodevelopment. Separate comparisons will be made at both trough and peak levels to allow examination of both acute and chronic effects.

*Hypothesis 2b:* Fetuses of B+N maintained mothers, as compared to a matched cohort of methadone exposed fetuses, will exhibit fetal heart rate and motor activity patterns indicative of greater fetal well-being.

*Aim 3:* Determine the differential effects on the infant's NAS expression in B+N as compared to the other two treatment exposures (matched methadone exposed and historical buprenorphine exposed infants).

*Hypothesis 3a:* B+N-exposed infants will have mild NAS

*Hypothesis #3b:* B+N exposed infants will have less severe NAS symptomatology than methadone exposed infants, consist with current literature.

*Hypothesis #3c:* B+N exposed infants will have similar NAS severity relative to buprenorphine-only exposed infants.

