*Infant study:* For hypothesis 4A, we will use descriptive statistics to characterize BN-exposed infants' NNNS scores on each of 13 summary scales; based on previous work we will focus on habituation, arousal, excitability, and hypertonicity. We will fit a model to determine if NNNS scores change over time during the first month of life, and we will fit an additional model with an interaction between infant sex and time to determine if sex affects NNNS trajectories. For hypothesis 4B, we will fit models where  $\text{NNNS}_{ij} = \beta_0 + \beta_1\text{BN} + \beta_2 \cdot \text{pX2\_p} + \varepsilon_{ij}$ , and  $\beta_1$  represents the difference, across timepoints in the NNNS between BN and methadone exposed infants. We will then fit a model where  $\text{NNNS}_{ij} = \beta_0 + \beta_1\text{BN} + \beta_2\text{time} + \beta_3\text{BN} * \text{time} + \beta_4 \cdot \text{pX4\_p} + \varepsilon_{ij}$ , where  $\beta_3$  represents the difference in NNNS trajectories over time between BN and methadone-exposed infants. For hypothesis 4C, we will fit analogous models to 4B, but with buprenorphine-exposed infants as the comparator. These models will be adjusted for maternal age, race, dosing, and other substance use.

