*Breastmilk study:* Basic descriptive statistics (mean, standard deviation, range) will be used to report concentrations of B+N in breast milk of lactating women on days 2-4, 14 and 30. Additional considerations for associations between maternal dose, maternal plasma and breast milk concentrations will be examined using linear regression. Descriptive statistics will be used to report plasma concentrations of B+N in breastfeeding infants and linear regression to evaluate potential associations between infant B+N plasma concentrations and maternal B+N dose. Although potentially underpowered, we will also fit linear regression models for associations between maternal dose, maternal plasma concentrations and breast milk concentrations with maternal dose as the main predictor. Although limited power exists for longitudinal models in this study due to small subject numbers, we will fit mixed effects models to examine changes over time in breast milk B+N concentrations for each sampling time. The analyses proposed here are not meant to be exhaustive and cannot be due to space limitations. However, they illustrate our approach for examining the relations among the complex set of independent, dependent, and confounding variables collected in this proposal.

*Computation of Power:* Sample size estimates for each study were premised with a power of .8, alpha =.05, and large effect sizes as observed in our prior studies (Jansson, 2005, 2007a), which were conducted with a similar experimental design. Based on a conservative estimate of 50% non-completion, the total number of participants to be enrolled will be 160. In comparison samples, we will have 40 for buprenorphine, and 40 for methadone. Using available pilot data, for hypothesis 1, we would have 80% power to detect a mean difference of 4.23 (SD 6.68) in peak/trough fetal heart rate. For the mixed effects models, via simulation using pilot data, we would be powered to detect a trajectory difference of .35 per week between groups. For hypothesis 2, we would have 80% power to detect a mean difference of 4.12 (SD 6.49) in peak fetal heart rate. For the mixed effects models, via simulation, we would be powered to detect a trajectory difference of .32 per week between BN and buprenorphine.

For hypothesis 3, we would have 80% power to detect a mean effect size of ..63 for difference in NAS severity between groups

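### No stated fetal model compares development with methadone: the trajectory models name buprenorphine only, and Hypothesis 2b uses week 36 alone

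*Combined protocol and SAP*

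**What the plan says.** Aim 2 (section 2) is to "Evaluate the development of the B+N-exposed fetus, and compare this with two other treatment exposures (a matched prospective methadone maintained group"; the second comparator it names is the historical group exposed to buprenorphine alone. Hypothesis 2a covers level and developmental trajectory against buprenorphine-only. Hypothesis 2b expects signs of greater well-being than in methadone-exposed fetuses and names neither a week nor a trajectory.

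Section 7b describes the models for Aims 1 and 2 as longitudinal mixed models with random intercepts. The Hypothesis 2a model with a BN-by-time term has a coefficient that "represents the difference in outcome trajectory over time between BN and Buprenorphine". The three-way model added under Hypothesis 1c is "to determine if changes over time in peak-trough differences vary between BN and Buprenorphine". The methadone comparison is: "For Hypothesis 2B, we will fit a model similar to 2A but only using data from 36 weeks to compare methadone and BN".

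The power text follows the same split: "we would be powered to detect a trajectory difference of .32 per week between BN and buprenorphine". For level it says: "For hypothesis 2, we would have 80% power to detect a mean difference of 4.12 (SD 6.49) in peak fetal heart rate".

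The infant plan is different. Hypothesis 4b fits BN by time against methadone, with a coefficient that "represents the difference in NNNS trajectories over time between BN and methadone-exposed infants".

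**The concern.** An aim that speaks of comparing development with two groups needs, for each group, a model that uses more than one gestational age. The plan writes such a model for one group only.

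The group left out is the stronger comparator. The methadone women are recruited concurrently and matched (the matching factor shown is route of administration), while the buprenorphine-only data date from 2012-2016. As written, the fetal trajectory is tested only against the group more open to period differences. The concurrent group gets a level test at 36 weeks and a test of the peak-trough differential. A trajectory comparison with methadone added after the data are seen would not be pre-specified, and with seven fetal measures at peak and trough there would be room for selection.

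A smaller point concerns the Hypothesis 2a level model, which contains BN and covariates but no gestational week. Women contribute one to four visits depending on entry, and the monitoring section says the outcomes change with gestation. If the visit mix differed from that of the historical group, the difference would enter the BN coefficient.

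**Working it through.** **Which between-group fetal models exist (section 7b)**

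| Model | Comparator | Can it show a group difference over gestation? |
|---|---|---|
| H1c, peak by BN | methadone or buprenorphine | No, it has no time term |
| H1c, peak by time by BN | buprenorphine | Yes, for the peak-trough difference |
| H2a, BN | buprenorphine | No |
| H2a, BN by time | buprenorphine | Yes |
| H2b, BN | methadone | No, week 36 only |

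The words "similar to 2A" in the H2b sentence cannot carry the BN-by-time model over, because time does not vary within one week. If peak and trough are fitted separately, as in H2a, each fetus gives one observation and the planned random intercept cannot be estimated.

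**The plan's own figures.** Inputs from *Computation of Power*: 40 per group, SD 6.49, alpha .05 (taken as two-sided), power .80.

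- Level: 4.12/6.49 = 0.635 SD. A two-sample t-test with 78 df has power 80.1%, so the stated figure is reproduced.
- Slope: visits at 24, 28, 32 and 36 weeks give Sxx = 36 + 4 + 4 + 36 = 80. With a random intercept and visit correlation r, SE = 6.49 × √(1 − r) × √(2/40) / √80. The documents do not give r. At r = 0.5, SE = 4.589 × 0.2236 / 8.944 = 0.115. Multiplying by 2.84 (78 df) gives a detectable slope of 0.325, which agrees with the stated .32. The plan's slope figure therefore fits four complete visits and r near 0.5.

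**Power of BN by time against methadone at .32 per week** (.32 × 12 = 3.84 over weeks 24 to 36). This uses generalised least squares with known variance, compound symmetry and 40 per arm. The visit mixes are assumptions, with late entrants missing the early weeks.

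| Women giving 4/3/2/1 visits | SE at r = .3/.5/.7 | Detectable slope | Power at .32 |
|---|---|---|---|
| 40/0/0/0 | .136/.115/.089 | .385/.325/.252 | 65/79/95% |
| 20/10/6/4 | .166/.143/.112 | .472/.405/.317 | 48/61/81% |
| 10/10/10/10 | .205/.178/.141 | .581/.505/.400 | 34/43/61% |

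A 3-df group-by-week test is weaker for the same linear difference: 48/63/86%, 33/43/66% and 22/29/44%.

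**What the 36-week test sees.** If the groups are equal at week 24 and diverge by .32 per week, the gap at week 36 is 3.84 and power is 74%. If the same slope difference leaves a gap of 1.92 at week 36, power is 26%. If the groups meet at week 36, the test has only its 5% error rate.

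**Would averaging over visits be better?** Across the same mixes and correlations, a visit-averaged contrast has power 83-98% if the difference is 4.12 at every week, 59-86% if it rises from 2.06 to 4.12, and 31-53% if it rises from 0 to 4.12. The 36-week test has 80% in all three cases. Neither is better in general.

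**H2a without a week term.** Suppose a fraction f of one group, and none of the other, is seen only at weeks 32 and 36, and everyone else gives four visits. The weighted mean gestational age shifts as follows for f = .1/.2/.3:

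- r = .3: .30/.62/.95 weeks
- r = .5: .34/.69/1.05 weeks
- r = .7: .37/.74/1.12 weeks

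At assumed slopes of 0.5 to 1.0 beats per minute per week, the bias runs from .30 × 0.5 = 0.15 to 1.12 × 1.0 = 1.12, against a detectable 4.12. With equal visit mixes it is zero.

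**The case against.** The hypotheses and models do agree with each other. Trajectory appears in H2a and not in H2b, and the 36-week contrast tests H2b as worded. The word development in the aim could mean developmental status and not slope. The plan also warns that "The analyses proposed here are not meant to be exhaustive and cannot be due to space limitations", and the power text for hypothesis 1 mentions a detectable .35 per week between groups without naming them, so the gap may be one of drafting.

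Much of this stands. H2b is met, and the gap is against Aim 2, not against H2b. But the non-exhaustive statement does not supply a model, and the buprenorphine counterpart is written out in full. The .35 line sits under hypothesis 1 and specifies no analysis. H4b shows that the investigators write the methadone trajectory model when they intend it.

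Three caveats also stand. The 4.12 figure is stated for hypothesis 2 without naming week 36 or methadone; applying it to H2b is an inference from the equal group sizes. The visit mixes cover late entry only, while sessions cancelled after a positive toxicology screen are a second source of missing visits. The H2a bias rests on an assumed imbalance that the documents do not show. The Background's statement that entry criteria were essentially the same across projects makes a large imbalance less likely, and the H2a trajectory model already contains time.

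**Conclusion.** The concern holds. No stated fetal model compares development with methadone, so part of Aim 2 has no analysis, and the concurrent recordings at weeks 24 to 32 go unused for that purpose. No stated power figure is wrong; both hypothesis 2 figures checked here are reproduced, the slope figure at an assumed correlation of 0.5.

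The missing test would have about the power the plan claims against buprenorphine if visits are complete and the correlation is near 0.5 (79%). It would have well below 80% if entry is late. These values rest on assumed correlations and visit mixes; the gap itself does not. The missing week term in H2a is a safeguard to add, not a demonstrated bias.

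**What to change.** - State for methadone the model H2a uses for buprenorphine: BN, time, BN by time and the stated covariates, with a random intercept, all visits, separately at peak and trough. Name the BN-by-time coefficient as the Aim 2 development comparison with methadone.
- Keep the 36-week contrast as the main H2b test and say why week 36 was chosen. With one observation per fetus, describe it as ordinary regression without a random intercept.
- A 3-df group-by-week version can serve as a sensitivity analysis, since the monitoring section reports a change in steepness between 28 and 32 weeks. A visit-averaged contrast can be secondary, with a note that it gains power only if the difference is roughly constant over weeks 24 to 36.
- Add gestational week to the H2a level model.

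The cost is SAP wording; no new participants or recordings are needed. It adds 7 measures × 2 (peak and trough) = 14 interaction tests. The SAP should say that a null slope result would not show equal development, particularly with late entry, and that the model treats missed visits as missing at random, which is less secure for sessions cancelled after a positive screen. If the sponsor does not want the model, the alternative is to limit the Aim 2 methadone comparison to 36 weeks.
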